3.2 Secondary Objectives

Secondary and exploratory objectives are to assess changes in the dyad's relationship functioning at the Midpoint and Primary Endpoints, assess changes in self- and CSO participant-reported PTSD symptoms in the PTSD+ participant, and assess problems that often co-occur with PTSD, such as depression, sleep disturbances, maladaptive beliefs about self and others, and emotion regulation difficulties.

- Assess changes in PTSD symptoms from baseline as measured by the CAPS in participants with chronic PTSD at Long-term Follow-up at 3 months and 6 months.
- Assess changes in self-reported PTSD symptoms from baseline as measured with the Posttraumatic Stress Disorder Checklist for the DSM-5 (PCL-5) at Baseline, at each Integrative Session, at the Midpoint, Primary Endpoint and Long-term Follow-up at 3 months and 6 months for both the PTSD+ participant and CSO participant (based on the (PTSD+ participant).
- Assess changes in depression symptoms from baseline with the Beck Depression Inventory-II (BDI-II) at Baseline, Midpoint, the Primary Endpoint, and Long-term Follow-up at 3 months and 6 months for both participants.
- Assess changes in self-reported sleep quality from baseline with the Pittsburgh Sleep Quality Index (PSQI) at Baseline, Midpoint, the Primary Endpoint, and Long-term Follow-up at 3 months and 6 months for both participants.
- Assess changes in self-reported posttraumatic growth from baseline with the Posttraumatic Growth Inventory (PTGI) by the PTSD+ participant and CSO participant (based on the PTSD+ participant) at the Midpoint, the Primary Endpoint, and Long-term Follow-up at 3 months and 6 months.
- Assess changes in psychological and physical aggression from baseline with the

- Revised Conflict Tactics Scale (CTS-2) at the Midpoint, Primary Endpoint, and Long-term Follow-up at 3 months and 6 months for both participants.
- Assess changes in emotional regulation from baseline with the Emotion Regulation Questionnaire (ERQ) at the Midpoint, Primary Endpoint, and Longterm Follow-up at 3 months and 6 months for both participants.
- Assess changes in compassion, empathy, and social functioning from baseline
 with the Interpersonal Reactivity Index (IRI) on the day after each Experimental
 Session, at Midpoint, Primary Endpoint, and Long-term Follow-up at 3 months
 and 6 months for both participants.

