The PSQI is a measure of self-reported sleep quality over a one-month period. The PSQI was designed to be a reliable, standardized measure able to distinguish between good and poor sleepers. It consists of 19 items, with possible responses ranging from 0 to 4 on a five-point scale [146]. The PSQI consists of seven sub-scales; sleep quality, sleep latency, sleep duration, habitual sleep efficiency, sleep disturbance, use of sleeping medications, and daytime dysfunction. These are all summed to produce a single global scale. Global scores can range from 0 to 21, with higher scores reflecting poorer sleep quality, and a score below five indicative of good sleep. It takes five to 10 minutes to complete. Test-retest reliability ranges from 0.85 to 0.87, and it is internally consistent, with a Cronbach's alpha of 0.83 [146, 147]. Global scores correlate with other measures of alertness and self-reported sleep quality [143]. The Pittsburgh Sleep Quality-PTSD Addendum [148] is a seven-item addendum for the PSQI that assesses disruptive nocturnal behavior specific to PTSD (e.g., hot flashes, nervousness, trauma nightmares). The PTSD+ participant will indicate the presence and severity of trauma-related sleep disturbances. Both the PTSD+ participant and the CSO participant will complete the PSQI according to Table 3: Time and Events.

The PTGI is a 21-item self-report measure of perceived growth or benefits occurring after a traumatic event. It contains five subscales: relationship to others, new possibilities, personal strength, spiritual change, and appreciation of life [149, 150]. In this study, participants will complete the PTGI in reference to the time since the trauma at Baseline, but will respond in reference to the beginning of their participation in the study on all subsequent occasions. PTGI sub-scale scores are reliable, with reliability coefficients ranging from 0.83 to 0.90, and the scale scores were moderately related to each other [149, 151]. PTGI scores are corroborated by others' assessments of posttraumatic growth, suggesting that the measure has convergent validity [152, 153]. Both the PTSD+ participant and the CSO participant will complete the PTGI according to Table 3: Time and Events.

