A blinded IR who will not be present during any of the therapy sessions will administer:

• Structured Clinical Interview for DSM-5 Diagnoses (Research Version) (SCID-RV) to assess eligibility based on Axis I diagnoses, which includes a self-report questionnaire to focus on modules to use based on symptoms for both the PTSD+participant and CSO participant

Page 43 of 89

- SCID-II Axis 2 questionnaire to determine if specific modules of the SCID-II Interview will be conducted to confirm diagnoses of personality disorders
- Last-month CAPS for the PTSD+ participant to assess PTSD symptoms and eligibility, which may be recorded to video in as many instances as necessary to establish inter-rater reliability

The following self-report measures will be completed:

- PTGI (in reference to time since the trauma) for the PTSD+ participant and modified for the CSO participant to rate the PTSD+ participant
- PCL-5 (last month) to assess PTSD symptoms for the PTSD+ participant and modified for the CSO participant to rate the PTSD+ participant.
- TABS to assess trauma related beliefs for the PTSD+ participant and modified for the CSO participant to rate the PTSD+ participant
- MDI to assess dissociative symptomology for the PTSD+ participant and CSO participant
- SORTS to assess partner accommodation for the CSO participant
- BDI-II to assess depression symptoms for both the PTSD+ participant and CSO participant
- PSQI to assess sleep quality for both the PTSD+ participant and CSO participant. PSQI-PTSD Addendum will be assessed for the PTSD+ participant only
- ERQ to assess emotional regulation for both the PTSD+ participant and CSO participant
- TAS-20 to assess emotion recognition, alexithymia for both the PTSD+ participant and CSO participant
- QRI to assess relationship satisfaction for both the PTSD+ participant and CSO participant
- CTS to assess conflict, tactics and aggression for both the PTSD+ participant and CSO participant
- IPF to assess psychosocial functioning for both the PTSD+ participant and CSO participant
- MSIS to assess social intimacy for both the PTSD+ participant and CSO participant
- IRI to assess compassion, empathy and social functioning for both the PTSD+ participant and CSO participant
- IPC for both the PTSD+ participant and CSO participant
- CSI for both the PTSD+ participant and CSO participant, if in a romantic relationship

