5.2.7 Evaluation and Preparation Visit at Midpoint (Visit 9 - Clinic Visit)

(Approximately 3 weeks after V3; prior to V10)

CBCT Manual Sessions 10 and 11

Sessions 10 and 11 – Making meaning of the trauma. Discussion of the themes of trust and control.

The midpoint evaluation will occur approximately 20 days after the first Experimental Session. Dyads who have withdrawn from treatment but have continued for follow-up will also complete this time point. This session will be recorded to audio/video.

- a. The therapists will assess suicidal ideation and behavior with the C-SSRS
- b. General Wellbeing will be assessed
- c. Collect AEs and medications, as described in Sections 8.0 and 9.0

The following self-report measures will be completed at the midpoint:

- PTGI (in reference to time since the trauma) for the PTSD+ participant and modified for the CSO participant to rate the PTSD+ participant
- PCL (since last visit) to assess PTSD symptoms for the PTSD+ participant and modified for the CSO participant to rate the PTSD+ participant
- TABS to assess trauma related beliefs for the PTSD+ participant and modified for the CSO participant to rate the PTSD+ participant
- MDI to assess dissociative symptomology for the PTSD+ participant and CSO participant
- SORTS to assess partner accommodation for the CSO participant
- BDI-II to assess depression symptoms for both the PTSD+ participant and CSO participant
- PSQI to assess sleep quality for both the PTSD+ participant and CSO participant.
 PSQI PTSD addendum will be completed by PTSD+ participant only
- ERQ to assess emotional regulation for both the PTSD+ participant and CSO participant
- TAS-20 to assess emotion recognition, alexithymia for both the PTSD+ participant and CSO participant
- QRI to assess relationship satisfaction for both the PTSD+ participant and CSO participant
- CTS to assess conflict, tactics and aggression for both the PTSD+ participant and CSO participant
- IPF to assess psychosocial functioning for both the PTSD+ participant and CSO participant
- MSIS to assess social intimacy for both the PTSD+ participant and CSO participant
- IRI to assess compassion, empathy and social functioning for both the PTSD+ participant and CSO participant

- IPC for both the PTSD+ participant and CSO participant
- CSI for both the PTSD+ participant and CSO participant, if in a romantic relationship

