# **Efficacy Analyses**

For all primary, secondary, and exploratory endpoints descriptive statistics (n, mean, standard deviation, median, range, effect size (for measures of interest), or frequencies and percentages where appropriate) will be provided for the total sample and by PTSD+ participants and CSO participants.

Effect size (Hedges' g) will be determined by calculating the mean difference pre- and post-treatment divided by the pooled weighted standard deviations for means at baseline and follow-up [3].

Hedges' 
$$g = (M_1 - M_2) / SD*_{pooled}$$

Where:

- $M_1 M_2 = \text{difference in means}$
- SD\*pooled = pooled and weighted standard deviations

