## 2. Secondary and Exploratory Efficacy Analyses

Efficacy of secondary and other exploratory outcome measures will be assessed at baseline, midpoint (visit 9), and primary endpoint (visit 16) to examine change in scores over time in the total sample, and separately, by PTSD+ participants and CSO participants.

For each model, a one-way repeated-measures ANOVA with post-hoc contrast comparisons will be conducted to test the effects of the treatment on: PTSD CAPS-5; Significant Others' Responses to Trauma Scale (SORTS); Posttraumatic Stress Disorder Checklist for the DSM-5 (PCL-5); Beck Depression Inventory-II (BDI-II); Emotion Regulation Questionnaire (ERQ); Pittsburgh Sleep Quality Index (PSQI); Posttraumatic Growth Inventory (PTGI); Toronto Alexithymia Scale-20 (TAS-20); Inventory of Psychosocial Functioning (IPF); Revised Conflict Tactics Scale (CTS-2); Trauma and Attachment Beliefs Scale (TABS); and Multiscale Dissociation Inventory (MDI). Relationship distress outcome measures include: Interpersonal Reactivity Index (IRI); Quality of Relationships Inventory (QRI); Miller Social Intimacy Scale (MSIS); Interpersonal Closeness Measure (IPC); and Couples Satisfaction Index (CSI).

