# 3. Secondary Efficacy Analyses at Secondary Endpoints (Long-Term Follow-up)

Efficacy of outcome measures for long-term follow-up will be assessed at baseline, midpoint (visit 9), primary endpoint (visit 16), 3-month follow-up (visit 17), and 6-month follow-up (Visit 18) to examine changes over time in the total sample, and separately, by PTSD+ participants and CSO participants.

For each model, a one-way repeated-measures ANCOVA with baseline scores as covariates and post-hoc contrast comparisons will be conducted to test the effects of the treatment on: PTSD CAPS-5; Significant Others' Responses to Trauma Scale (SORTS); Posttraumatic Stress Disorder Checklist for the DSM-5 (PCL-5); Beck Depression Inventory-II (BDI-II); Emotion Regulation Questionnaire (ERQ); Pittsburgh Sleep Quality Index (PSQI); Posttraumatic Growth Inventory (PTGI); Toronto Alexithymia Scale-20 (TAS-20); Inventory of Psychosocial Functioning (IPF); Revised Conflict Tactics Scale (CTS-2); Trauma and Attachment Beliefs Scale (TABS); and Multiscale Dissociation Inventory (MDI). Relationship distress outcome measures include: Interpersonal Reactivity Index (IRI); Quality of Relationships Inventory (QRI); Miller Social Intimacy Scale (MSIS); Interpersonal Closeness Measure (IPC); and Couples Satisfaction Index (CSI).

If data is missing from participant dropouts a mixed effect model repeat measures (MMRM) will be used instead of an ANCOVA.

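### Protocol section 5.1.1 moves the PTGI reference point to study start after Baseline while the visit sections keep it at the trauma; if 5.1.1 is followed, the planned PTGI change from baseline compares two different intervals

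*Protocol*

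**What the plan says.** **Protocol 5.1.1** sets two reference periods. At Baseline, "participants will complete the PTGI in reference to the time since the trauma at Baseline"; after that, they "will respond in reference to the beginning of their participation in the study on all subsequent occasions".

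**Protocol 5.2.1 (screening and Baseline)** agrees with 5.1.1 for that visit: "PTGI (in reference to time since the trauma) for the PTSD+ participant".

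**Protocol 5.2.7 (Midpoint, Visit 9)** keeps the same reference point after Baseline: "PTGI (in reference to time since the trauma) for the PTSD+ participant and modified for the CSO participant". Sections 5.2.8 (Visit 16) and 5.2.9 (Visits 17 and 18) repeat this instruction.

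**The objective** is a change score. Protocol 3.2 has "Assess changes in self-reported posttraumatic growth from baseline with the Posttraumatic Growth Inventory (PTGI"), at Midpoint, Primary Endpoint and both long-term follow-ups. SAP 3.2 carries the same objective.

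**The SAP analysis** has three parts that include the PTGI:
- For Baseline, Visit 9 and Visit 16 (Secondary and Exploratory Efficacy Analyses): "a one-way repeated-measures ANOVA with post-hoc contrast comparisons will be conducted to test the effects of the treatment on" a list of measures that includes the PTGI.
- For long-term follow-up: "a one-way repeated-measures ANCOVA with baseline scores as covariates and post-hoc contrast comparisons will be conducted", again with the PTGI listed.
- The effect size is obtained by "calculating the mean difference pre- and post-treatment divided by the pooled weighted standard deviations".

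The SAP does not mention the PTGI reference period.

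**The concern.** A change from baseline needs the same quantity at both ends. Under 5.1.1 the Baseline score is growth between the trauma and enrolment, and every later score is growth since enrolment. These intervals do not overlap, and for chronic PTSD the first may be far longer. A participant who reported substantial growth before enrolment and some further growth on study could then show a fall, and the trial could report a decline in posttraumatic growth where there was a gain.

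The concerned significant other (CSO) rates the PTSD+ participant on a modified PTGI at the same visits, so the conflict reaches both sets of PTGI results.

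**Working it through.** **Figures in the plan.** There is no PTGI figure to reproduce; Protocol 12.1 says that power was not available for secondary and exploratory measures. The only power figure is 62% for CAPS-5. A two-sided paired t-test with n = 10, effect size 0.8 and alpha 0.05 has 9 degrees of freedom and noncentrality 0.8 × √10 = 2.53, which gives 61.6%. That figure reproduces and does not bear on this point.

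**Step 1: instructions side by side.**

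| Visit | Section 5.1.1 | Visit section |
|---|---|---|
| Baseline | since the trauma | since the trauma (5.2.1) |
| 9 | since study start | since the trauma (5.2.7) |
| 16 | since study start | since the trauma (5.2.8) |
| 17, 18 | since study start | since the trauma (5.2.9) |

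The sections agree at Baseline and conflict at all four later PTGI visits.

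**Step 2: what each version estimates.** Let T0 be the Baseline score for growth since the trauma, T1 the score for growth since the trauma at a later visit, and S1 the score for growth since study start at that same visit.
- Visit sections: change = T1 - T0.
- Section 5.1.1: change = S1 - T0.
- Difference between the two: T1 - S1.

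This holds whatever the scoring. Its size depends on how the two later ratings relate, and the documents do not say.

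**Step 3: illustration.** Assume additive scores, T1 = B + D and S1 = D, where B = T0 is baseline growth and D is on-study growth. The visit sections give (B + D) - B = D, and section 5.1.1 gives D - B. The values of B and D are assumed.

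| B | D | Constant reference | Section 5.1.1 |
|---|---|---|---|
| 20 | 10 | +10 | -10 |
| 40 | 10 | +10 | -30 |
| 60 | 10 | +10 | -50 |
| 40 | 20 | +20 | -20 |
| 20 | 40 | +40 | +20 |

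Under additivity the sign is wrong whenever 0 < D < B. When D exceeds B, as in the last row, the sign is right and the size is too small.

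**Step 4: which analyses are touched if 5.1.1 is followed.**
- Change from baseline (Protocol 3.2, SAP 3.2): affected.
- Repeated-measures ANOVA over Baseline, Visit 9 and Visit 16: the contrasts against Baseline are affected; Visit 9 against Visit 16 is not.
- Pre/post Hedges' g: affected.
- Long-term ANCOVA: baseline used only as a covariate is not a problem, because a covariate need not share the outcome's reference period. That SAP section also lists Baseline among its time points, so any contrast there against Baseline would be affected.

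**The case against.** The strongest reply is that the harm hangs on one sentence. Every visit procedure that names the PTGI, Baseline included, uses the trauma as the reference. If staff work from the visit sections, the reference period is constant and the planned change is interpretable. The CRF instruction is not in the documents, so what participants actually see is unknown. This stands, and it makes the bias conditional. It does not remove the contradiction, since neither document ranks the sections.

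A reader might also infer more than the documents support:
- *That a participant with no on-study growth would score near zero at follow-up.* This needs items that start at 0. Section 5.1.1 gives 21 items but no response anchors; if items started at 1, the lowest total would be 21.
- *That the change is wrong by exactly the full baseline score.* This follows only under additivity. On a bounded scale, the since-the-trauma change could itself fall short of on-study growth.
- *That all PTGI analyses fail.* Comparisons among post-baseline visits and covariate-only use of baseline do not.
- *That the plan has different post-baseline visits use different wording.* Each instruction is constant across those visits; mixing would require staff to switch between sources.

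Finally, the PTGI is one of many secondary measures, listed under exploratory objectives in the SAP of a 10-dyad study not intended to lead to registration. That limits the importance of the point, not its correctness.

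**Conclusion.** The contradiction is certain from the text: section 5.1.1 and the visit sections give different PTGI reference periods at Visits 9, 16, 17 and 18. The consequence is conditional on 5.1.1 being followed. In that case the change from baseline, the ANOVA contrasts against Baseline and the pre/post Hedges' g do not measure change in one quantity.

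The size cannot be stated from the documents. Under the additive assumption, baseline growth of 20 to 60 with on-study growth of 10 turns +10 into -10 to -50. It would be going too far to conclude that the PTGI results will be biased, or by how much. The CAPS-5 primary analysis and its stated power are untouched. The point should be corrected because it is cheap to correct and an uncorrected result could point the wrong way.

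**What to change.** **Preferred:** use the time since the trauma at all visits. Delete the re-anchoring clause in 5.1.1, make the CRF instruction match for both the PTSD+ and the CSO versions, and state the reference period in the SAP. The planned change-from-baseline analysis then stands. The cost is one protocol clause, one CRF instruction and one SAP line, with no added assessments.

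**Alternative:** if the follow-up scores are meant to capture growth since study start, align 5.2.7 to 5.2.9 with 5.1.1, drop the PTGI baseline contrasts and pre/post Hedges' g, and summarise the follow-up scores on their own. Baseline may remain only as a covariate. This costs more editing: the three visit sections, the PTGI objective in Protocol 3.2 and SAP 3.2, and the SAP's effect-size, ANOVA and long-term follow-up text.

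Under either option, if any post-baseline PTGI forms have already been completed, establish which wording they carried before analysis.

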	Screen	Preparat	tory	Experimental Session 1, Integrative Sessions Midpoint Experimental Session 2, Inte					Integrative	e Sessions		Primary Assess	3 Mo LTFU	6 Mo LTFU					
Visit #	Pre-Study	V 1	V 2	V3	V 4	V 5	V6	V 7	V 8	V9	V10	V11	V12	V13	V14	V15	V16	V17	V18
Type of Session	Screening	Prep	Prep	Exp	Int	Int	Int	Int	Int	Assess /Prep	Exp	Int	Int	Int	Int	Int	Outcome	Assess	Assess
Visit Format	Telemed or Visit	Telemed	Visit	Visit (overnight)	Visit	Telemed	Telemed	Telemed	Telemed	Visit	Visit (overnight)	Visit	Telemed	Telemed	Telemed	Telemed	Telemed	Telemed	Telemed
Visit Timing Window	>1 day, month prior to Visit 1	≤ 1 Mo before V2 ^J	Day 0	Day 1	Day2	over 3 w	4 vis eeks betw		nd V10	~3 weeks post V3; prior to V10	~3 weeks post V3	1 day post V10	over 4	4 v weeks betv	risits veen V10	and V15	1 Mo post V15	3 Mo post V15	6 Mo post V15
CBCT Manual Session #			1, 2, 3	4, 5 – Condensed delivery just after MDMA administration	Review	6	7	8	9	10, 11	Review	Review	12	13	14	15			
Initial Phone Screen	✓																		
Informed Consent	✓																		
Medical/Psychiatric History (Medical Record Review)	✓																		
General Phys. Exam (BP, Pulse, Temp)	✓A																		
Brief Neurological Exam	✓																		
ECG	✓																		
SCID-RV	✓																		
Clinical Lab Tests, w/ HIV, HCV test	✓A																		
Collect Concomitant Medication	✓	✓	✓	✓	✓	✓	✓	✓	✓	✓	✓	✓	✓	✓	✓	✓	✓	✓	
Medication Taper (if applicable)		✓																	
Study Enrollment after meeting I/E		✓	✓																
Record to Audio/Video		✓	✓	✓	✓	✓	✓	✓	✓	✓	✓	✓	✓	✓	✓	✓	✓	✓	
Drug Screen	✓A			✓							✓								
Pregnancy Screen (if applicable)	✓A			✓							✓								
Administer IP Drug + Therapy/CBCT				✓							✓								
Integrative Session					✓	✓	✓	✓	✓			✓	✓	√	✓	✓			
Issue Out of Session Assignments				✓	✓	✓	✓	✓	✓		✓	✓	✓	√	✓				
7 days of Telephone Contact					✓ G	✓ G	✓ G					✓ G	✓ G	✓ G					
CAPS ^I	✓																✓	✓	✓
PCL individual and participant	✓		✓		✓	✓	~	√	√	√		✓	✓	✓	√	✓	✓	✓	✓
BDI-II	✓									✓							✓	✓	✓
IRI	✓				✓					✓		✓				Ī	✓	✓	✓
General Wellbeing	✓	✓	✓	✓	✓	✓	✓	✓	✓	✓	✓	✓	✓	✓	✓	✓	✓	✓	✓
TAS-20, QRI, SORTS, CTS-2, IPF, MSIS, TABS, MDI, ERQ, PSQI, PTGI, CSI	√									√							✓	√	√
LTFU Questionnaire																		✓	✓
IPC	✓			✓C						✓	✓C						✓	✓	✓
RRPQ																	✓		
Vitals (Monitoring of BP, Pulse and Temp)				✓							✓								
Changes in Tinnitus and/or Pain H	✓	✓ D	✓ D	✓ D	✓ D	✓ D	✓ D	✓ D	✓ D	✓	✓ D	✓ D	✓ D	✓ D	✓ D	✓ D	✓	✓	✓

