	Wellbeing			calls		

Baseline = During 1-month screening period prior to enrollment day.

Midpoint = 2 weeks after 1st Experimental Session.

Primary Endpoint = 1 month post Visit 15.

LTFU 3, 6 = 3 months and 6 months after Visit 15.

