The Significant Others' Responses to Trauma Scale (SORTS) [9] is a 14-item self-report measure of relationship problems and psychological distress faced by partners of people with PTSD. Each behavior or issue listed is rated on a five-point Likert scale (anchored at 0-4) for frequency of the behavior or issue and degree of distress the behavior or issue causes for the partner. The SORTS demonstrates strong internal consistency. It has Cronbach's alpha for the total scale of 0.93 and alphas of 0.86 for frequency and 0.87 for intensity (degree of distress) scores, and associations with individual and relationship distress, including a positive correlation between SORTS score and PTSD symptom severity in the partner with PTSD, and between SORTS score and depressive symptoms in the partner without PTSD. The PTSD+ participant and the CSO participant will complete the SORTS about the PTSD+ participant according to Table 3: Time and Events.

The Revised Conflict Tactics Scale [161] is a widely used measure of physical, psychological, and sexual aggression as well as injury and negotiation between partners. The scale consists of 39 conflict tactics, with respondents indicating the frequency with which they and their partner engage in each tactic, with each item presented as a "self" and "partner". Responses are given on a seven-point Likert scale where 0 = "This has never happened" and 6 = "More than 20 times in the past month", with 7 indicating occurrence in the past but not in the past year. The CTS2 contains four subscales; negotiation, psychological aggression, physical assault, and sexual coercion, and an injury score assessing impact of violence. CTS2 subscales are internally consistent, with alpha coefficients ranging from 0.79 to 0.95. Examining responses from relationship partners indicates high rates of agreement on responses. The CTS2 demonstrated construct validity, with scales demonstrating correlations with selected outcomes (for

instance, assault scale with injury). Research in a sample from a batterer-intervention program found moderate to good test-retest reliability (from 0.60 to 0.79) for all scales save sexual coercion [162]. Both the PTSD+ participant and the CSO participant will complete the CTS-2 according to Table 3: Time and Events.

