The Trauma and Attachment Beliefs Scale (TABS) was developed as a brief self-report measure of maladaptive beliefs about current life circumstances that may occur following trauma exposure [167]. The measure consists of 15 items, with responses made on a seven-point Likert scale with 1 = not at all true for you and 7 = completely true for you. This scale assesses maladaptive beliefs within three domains: (a) threat of harm, (b) self-worth and judgment, and (c) reliability and trustworthiness of others. After following procedures for reverse-scored items, scores are summed to produce scale scores for each domain. The TABS has an overall reliability of alpha of 0.82, with scale reliability ranging from 0.71 to 0.76. TABS scores exhibit a positive association with CAPS global severity scores, particularly for the Threat of Harm scale, and the scale had a negative association with scores on the PTGI. Both the PTSD+ participant and the CSO participant will complete the TABS according to Table 3: Time and Events. The CSO participant will complete a modified version.

The Multiscale Dissociation Inventory (MDI) is a 30-item self-report test of dissociative symptomatology in the last month, with responses made along a five-point Likert scale, with 1 = never and 5 = very often. It is fully standardized and normed, and measures six different type of dissociative response: disengagement, depersonalization, derealization, emotional constriction / numbing, memory disturbance, and identity dissociation. A total

dissociation score can also be calculated. Reliability for each subscale various from 0.74 for memory disturbance to 0.91 for derealization. The MDI has been found to have good psychometric qualities in both the normative and validation samples [168-170]. Both the PTSD+ participant and the CSO participant will complete the MDI according to Table 3: Time and Events.

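### The CTS-2 response codes mix a past-month and a past-year recall, and the one-month PSQI and MDI windows at midpoint reach back before the first MDMA session

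*Protocol*

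**What the plan says.** **CTS-2.** Protocol section 5.1.1 assigns 0 to an act that never happened, then "6 = 'More than 20 times in the past month', with 7 indicating occurrence in the past but not in the past year". Codes 1 to 5 are not spelled out. Table 4 lists an edited form built on the psychological and physical aggression subscales and gives no recall period. Neither document says how code 7 is scored. Protocol section 3.2 makes change in aggression from baseline an objective at Midpoint, Primary Endpoint and both follow-ups.

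**PSQI and MDI.** The same section says "The PSQI is a measure of self-reported sleep quality over a one-month period" and calls the MDI a "30-item self-report test of dissociative symptomatology in the last month". Section 5.2.7 gives both at midpoint ("PSQI to assess sleep quality for both the PTSD+ participant and CSO participant"; the MDI and CTS are in the same list). It also switches the PCL to recall since the last visit. No such switch is stated for the PSQI, MDI or CTS-2.

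**Midpoint timing.** There are three statements:
- Section 5.2.7: "The midpoint evaluation will occur approximately 20 days after the first Experimental Session"
- Table 3, as an approximate timing: "3 weeks post V3; prior to V10"
- Note under Table 4: "Midpoint = 2 weeks after 1st Experimental Session"

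**Analysis.** SAP section 2 says the secondary measures "will be assessed at baseline, midpoint (visit 9), and primary endpoint (visit 16) to examine change in scores over time", using a repeated-measures ANOVA with post-hoc contrasts. SAP section 3 keeps midpoint in the long-term model.

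**The concern.** A change score needs a known recall period, and a post-treatment score should describe post-treatment time. The CTS-2 fails the first condition. Its two anchors imply different periods, and each reading harms the aggression objective in its own way: one has a gap in the codes, the other carries pre-treatment months into every post-treatment score.

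The PSQI and MDI fail the second condition, at midpoint only. If benefit starts at the first session, the baseline-to-midpoint contrast is too small and the midpoint-to-endpoint contrast too large. That second interval contains the second MDMA session, whose default dose is higher, so a reader could take the difference for added benefit of that session.

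**Working it through.** The documents give no figure for recall overlap. Their only power figure is for CAPS: 62% at d = 0.8, N = 10, two-sided 0.05. The noncentral t distribution (9 df, noncentrality 0.8 × √10 = 2.53) gives 61.6%, which reproduces it. The point does not depend on that figure.

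**Timeline, in days after Visit 3 (first MDMA session)**
- Visit 9: 14, 20 or 21 (the three statements above)
- Visit 10: about 21 (Table 3)
- Visit 15: 21 + 28 = 49 (section 5.2.6)
- Visit 16: 49 + 30 = 79, or 77 to 86 with its window (section 5.2.8)
- Visit 17: 49 + 91 = 140; Visit 18: 49 + 182 = 231 (section 5.2.9)

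**CTS-2, month frame.** Take a dyad whose aggression stopped at Visit 3. From Visit 16 on, code 0 is false because it did happen. Codes up to 6 are false because nothing happened in the past month. Code 7 is false because it happened within the past year: even at Visit 18 only 231 days have passed, fewer than 365. No code fits. If the respondent picks 7 and it is summed raw, an item scored 1 to 6 at baseline rises to 7.

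**CTS-2, year frame.** Share before Visit 3 = (365 − days since Visit 3) / 365.

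| Visit | Day | Share before Visit 3 |
|---|---|---|
| 9 | 20 | 345/365 = 95% (94–96% over days 14–21) |
| 16 | 79 | 286/365 = 78% (76–79% over its window) |
| 17 | 140 | 225/365 = 62% |
| 18 | 231 | 134/365 = 37% (36% if day 232) |

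Protocol section 4.1 instead counts follow-up from the primary assessment. Visit 18 would then be day 79 + 182 = 261, and the share 104/365 = 28%.

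**One-month windows at midpoint (PSQI, MDI, past-month CTS-2).** Share before Visit 3 = (window − day) / window.

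| Midpoint | 28-day month | 30-day month | 31-day month |
|---|---|---|---|
| Day 14 | 14/28 = 50% | 16/30 = 53% | 17/31 = 55% |
| Day 20 | 8/28 = 29% | 10/30 = 33% | 11/31 = 35% |
| Day 21 | 7/28 = 25% | 9/30 = 30% | 10/31 = 32% |

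At Visit 16 the month runs from about day 49 to day 79, after both MDMA sessions. The share before Visit 3 is 0% there and at Visits 17 and 18.

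**What this could do to the contrasts.** Assume a 30-day window that respondents average evenly, and midpoint at day 20.
- Full benefit at Visit 3, then stable: midpoint shows 20/30 = 67% of the change, and 33% moves to the later interval. At day 14 the figures are 47% and 53%.
- Benefit rising linearly from Visit 3 to Visit 15 (day 49): a 30-day recall shows 0.136 of the final change and a since-Visit-3 recall 0.204. The overlap moves 0.204 − 0.136 = 0.068, about 7%.

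Borrowing d = 0.8 for illustration only, the first case gives 0.8 × 0.67 = 0.53 at midpoint and leaves 0.27 for the later interval.

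**The case against.** **The CTS-2 form is not visible.** Section 5.1.1 describes the general scale while the study uses an edited one, so its actual labels may be sound. This is fair, but the protocol gives no other recall period, and the quoted anchors are what the site and the statistician have to work from. The reversed score depends on summing code 7 raw, which neither document prescribes or rules out.

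**A reader might infer that CTS-2 change is diluted at every visit, or that the aggression question cannot be answered.** The documents support neither. Under a month frame, Visits 16 to 18 contain no time before Visit 3. Under a year frame, most of the Visit 18 window is post-treatment: the change is attenuated but not lost.

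**A reader might infer that any midpoint-to-endpoint gain on the PSQI or MDI is spurious.** That needs full benefit at Visit 3 and even averaging over the month, and the documents establish neither. CBCT continues through Visit 15, so later gains may be real; recall weighted to recent days would shrink the overlap effect. The d of 0.8 is the CAPS planning value, and Protocol section 12.1 says no power estimates were available for secondary measures. The SAP does not itself attribute this change to the second session.

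**A reader might infer that medication washout fills the overlap.** Section 9.0 requires one week of stabilization after washout. With midpoint at day 20, washout could occupy at most 10 − 7 = 3 of the 30 days, and only in participants who taper.

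**Midpoint change is a stated objective**, so dropping its test is more than SAP wording. This stands and is reflected in the fix.

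**Conclusion.** The point holds in two parts.

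The CTS-2 recall is contradictory as written, and both readings harm the aggression objective. The month frame has no code for aggression that stopped 1 to 12 months earlier. The year frame places about 95%, 78%, 62% and 36–37% of recall before the first session at Visits 9, 16, 17 and 18. Dilution at Visit 16 and later applies only under the year frame.

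The PSQI and MDI windows overlap pre-treatment time at midpoint under all three stated timings: 25–35% at day 20–21, 50–55% at two weeks. The overlap follows from the dates alone. Its effect on the contrasts depends on when benefit starts and how recall is weighted, and ranges from about 7% to 33% of the final change in the two day-20 examples.

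PSQI and MDI changes from baseline to Visits 16, 17 and 18 are unaffected. So is the primary CAPS test, because CAPS is not given at midpoint and its one-month window at Visit 16 lies after both sessions. These are secondary scales in a ten-dyad pilot, but the repair is cheap and should be made.

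**What to change.** 1. **CTS-2.** Use one past-month frame at every visit, baseline included. Reword code 7 as *not in the past month, but it happened before that*, and count it as zero in the frequency total. State this in the protocol and SAP. Cost: less comparability with the unedited scale (the protocol already uses an edited form), and probably more zeros on severe items.
2. **Midpoint timing.** Reconcile the three statements, since they set the size of the overlap.
3. **Tested contrasts.** For the PSQI, MDI and CTS-2, test baseline to Visits 16, 17 and 18 in SAP sections 2 and 3. Report Visit 9 descriptively with the overlap stated. Cost: no midpoint test on three scales, and the midpoint objectives in Protocol section 3.2 and SAP section 3.2 must be amended to match.
4. **Alternative to 3.** Use recall since the first session at Visit 9, in the way the PCL recall is already shortened there. Cost: a shorter window than at baseline. For CTS-2 counts this alone lowers the score, so descriptive reporting suits that scale better.
5. **Interpretation.** State in the SAP that change from Visit 9 to Visit 16 on these scales will not be read as added benefit of the second session.
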